## .

## 7.2.4 Missing Data

MMTTs are performed in Cohort 2 subjects and will require a minimum of two timepoints in order to be considered evaluable. Any missing timepoints will be imputed using the following rules:

For C-peptide and blood glucose values:

- If the final timepoint is missing, it will be imputed as the average of the last available timepoint and zero (the value '0'). If consecutive, final timepoints are missing, this function will be performed twice (once for each timepoint).
- If a middle timepoint is missing, it will be imputed as the average the two neighboring timepoints. If consecutive, middle timepoints are missing, both values will be imputed as the average of the two closest, neighboring values on each side.

## C-peptide value only:

- If the 0 minute timepoint is missing, the value will be imputed as zero (the value '0'). If multiple timepoints were missed at the start of an MMTT, the timepoints will be imputed in reverse order (starting with the latest missing timepoint). The missing timepoint(s) will be imputed as one-half the value of the subsequent timepoint.

## Blood glucose value only:

- If a first timepoint is missing, the value will be imputed as the average of the first available timepoint and zero (the value '0'). If multiple timepoints were missed at the start of an MMTT, the timepoints will be imputed using this same formula, in reverse order (starting with the latest missing timepoint and repeating for each subsequent missing value until the 0 minute timepoint has been imputed).

For AEs, it is expected that complete start and end dates will be provided for all reported AEs. Therefore, no imputation for missing or partial dates is needed for AEs. No additional imputations will be performed for any other missing data in this study.

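### SAP 7.2.4 imputes a missing first or final MMTT glucose as half its neighbour, and 7.2.6.3.2 does not limit the second insulin-independence definition to measured glucose

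*SAP*

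**What the plan says.** SAP 7.2.4 opens its MMTT rules without restriction: "Any missing timepoints will be imputed using the following rules". For both C-peptide and glucose, "If the final timepoint is missing, it will be imputed as the average of the last available timepoint and zero". If several consecutive final samples are missing, "this function will be performed twice (once for each timepoint)". For glucose at the start of the test, "If a first timepoint is missing, the value will be imputed as the average of the first available timepoint and zero", with the step "repeating for each subsequent missing value until the 0 minute timepoint has been imputed". A missing middle sample is the mean of its neighbours. The section ends by ruling out imputation of any other missing data.

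SAP 7.2.6.3.2 gives two definitions of insulin independence. The first needs at least 14 consecutive logged days at zero insulin. The second adds three conditions: HbA1c of at most 7.0%, a glucose at the start of the MMTT of at most 125 mg/dL, and a 120-minute glucose of at most 180 mg/dL. The HbA1c and glucose values come from the clinic visit nearest in time to the zero-insulin period. The section says that blank insulin-log days do not count as zero. It makes no corresponding statement about missing or imputed glucose.

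**The concern.** Averaging with zero may be defensible for C-peptide in subjects selected for having almost none. It is not a sensible model for blood glucose, which stays well above zero. The 0-minute sample, and in a 2-hour test the 120-minute sample, are the end samples to which this rule applies. They are also the two values that 7.2.6.3.2 compares with a cut-off. The SAP defines no glucose AUC and no other derivation from MMTT glucose, so these cut-offs are the only place where the rule has a stated consequence. A subject could be reported as insulin-independent under the stricter definition on a glucose that nobody measured, and that might have failed if it had been. With few responders likely, each reported success should rest on observed data.

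**Working it through.** The plan states no figure to reproduce here, so the check applies its rules to its own cut-offs.

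**Inputs**
- End-sample rule (SAP 7.2.4): imputed value = (adjacent value + 0)/2.
- Middle-sample rule (SAP 7.2.4): mean of the two neighbours.
- Cut-offs (SAP 7.2.6.3.2): fasting at most 125 mg/dL; 120-minute at most 180 mg/dL.
- 2-hour MMTT (Protocol 7.2.2; Weeks 8, 12, 16, 20, 39): samples at 0, 30, 60, 90 and 120 minutes, so 120 minutes is the final sample.
- 4-hour MMTT (Protocol 7.2.1; Screening, Weeks 26 and 52/ET): samples also at 180 and 240 minutes, so 120 minutes is a middle sample.
- Site fasting glucose needed to start a test (Protocol 7.2): 70 to 200 mg/dL.

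**Limits with one sample missing**

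| Missing sample | Imputed value | Passes when |
|---|---|---|
| 0 min, either test | 30-minute value / 2 | 30-minute value ≤ 2 × 125 = 250 mg/dL |
| 120 min, 2-hour test | 90-minute value / 2 | 90-minute value ≤ 2 × 180 = 360 mg/dL |
| 120 min, 4-hour test | mean of 90- and 180-minute values | that mean ≤ 180; no halving |

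A 90-minute value of 320 in a 2-hour test, for example, gives 320/2 = 160, a pass.

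**Direction of error.** A 30-minute value above 250 imputes a fasting value above 125, which fails even if the true fasting value would have passed. A 30-minute value below 140 imputes a fasting value below 140/2 = 70 mg/dL, under the protocol's own floor for starting the test. Because of the 200 mg/dL ceiling, a false fasting pass concerns true fasting values of about 126 to 200 mg/dL.

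**Illustration (assumed 2-hour profile, mg/dL): 160, 220, 270, 290, 280.**
- All measured: fasting 160 and 120-minute 280; both fail.
- 0 and 120 minutes missing: 220/2 = 110 and 290/2 = 145; both pass.
- Only one of them missing: that criterion passes and the other, being measured, still fails.
- Same values in a 4-hour test, with 250 at 180 minutes and only 120 minutes missing: (290 + 250)/2 = 270; fails.

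**Does another rule supply the missing value?** SAP 7.2.6.1 maps unscheduled samples to scheduled times, but it is worded for AUC calculation and then refers to C-peptide, so as written it does not fill a missing glucose. Protocol 7.2 requires a site fasting glucose before the test, but the SAP does not use it in place of a missing 0-minute sample.

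**The case against.** The strongest reply is that 7.2.6.3.2 already means measured values. It speaks of values obtained at a visit and selects the value nearest in time. A sample that was not drawn was not obtained, so the nearest measured value would be used. This reading is plausible and may be what the authors intended. But the wording selects a visit and does not set aside the instruction in 7.2.4 to impute any missing timepoint. It would also leave the glucose rule in 7.2.4 with no stated use. The text supports both readings, and they can classify a subject differently.

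The second reply is that the event is rare, and this stands. A false pass needs 14 logged zero-insulin days, HbA1c of at most 7.0%, a missing 0- or 120-minute sample at the relevant MMTT, and a true value on the other side of the cut-off. Neither insulin nor HbA1c can be imputed. Protocol 7.2 lets an MMTT be rescheduled within its window, and Protocol 6.15 allows one at an unplanned visit.

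A reader might infer that the Fisher's exact test of insulin independence is compromised. The documents do not support that. SAP 7.3.7.3 does not say which definition is tested. Its follow-on percentage, HbA1c of at most 7.0% among independent subjects, would be 100% by construction under the second definition, so that part fits the first, which uses no MMTT glucose.

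A reader might also extend the point to the primary C-peptide endpoint, since an MMTT "will require a minimum of two timepoints in order to be considered evaluable". That does not follow from this glucose argument, and the documents do not show how often samples are missing. One separate, minor ambiguity exists: when several start samples are missing, the 0-minute C-peptide could be zero ("If the 0 minute timepoint is missing, the value will be imputed as zero") or half the next value ("The missing timepoint(s) will be imputed as one-half the value of the subsequent timepoint"). It deserves a clarifying sentence but is not part of this point.

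**Conclusion.** The point holds as a gap between two sections with a definite consequence if 7.2.4 is applied literally. An unmeasured glucose can meet the second insulin-independence definition when the adjacent value is as high as 250 mg/dL (fasting) or 360 mg/dL (120 minutes, 2-hour test). It can also produce a false failure. The 360 limit does not apply to a lone missing 120-minute sample in a 4-hour test.

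The harm is a possible, probably rare, misclassification in a reported count for the second definition only. If Cohort 2 reaches its maximum of 40, one subject is 1/40 = 2.5 percentage points, and more within a treatment group, whose sizes are not given. The expected number affected cannot be estimated. The secondary p-values are described as descriptive and SAP 7.1 says no hypotheses are tested, so no formal conclusion turns on this. It would go too far to say that independence will be overstated: the documents show that a false pass is possible, not that one will occur or that errors favour the product. The point should still be fixed, because the rule is physiologically unsound where it acts and correction is cheap.

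**What to change.** In SAP 7.2.6.3.2, with a cross-reference in 7.2.4, state that only measured 0- and 120-minute MMTT glucose values can satisfy the second definition, and that values imputed under 7.2.4 are not used for it. Before database lock, specify how a subject with a missing required value at the nearest MMTT is classified (for example, criterion not met), and report the number of subjects affected.

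The cost is a few sentences of SAP wording and one reported count; no data collection changes. The downside is that a truly independent subject with a missing sample may be counted as not independent under the second definition. The reported count makes that visible. The glucose rule in 7.2.4 would then have no stated use, so the cross-reference should say whether it is kept and for what.

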## 7.2.5 Change From Baseline

Change from baseline is defined as:

Value of parameter post-baseline – Value of parameter at baseline

If the post-baseline value for a specific parameter at a specific timepoint is missing, then the change from baseline at that timepoint will not be calculated. The subject will not be included in the change from baseline at that timepoint, for that parameter (but will be included in the change from baseline for other timepoints where the subject has post-baseline data for that same parameter).

#### 7.2.6 Data Derivations and Transformations

## 7.2.6.1 C-peptide AUC0-4h and AUC0-2h

Cohort 2 subjects will undergo MMTTs. The area under the curve (AUC) for each MMTT is calculated by adding the areas under the curve between each pair of consecutive observations. The calculation is based on the trapezoidal rule:

$$AUC = \frac{1}{2} \sum_{i=1}^{n-1} (t_{i+1} - t_i) (y_i + y_{i+1})$$

Where there are n C-peptide measurements  $y_i$  at nominal time points  $t_i$  (i=0,...,n-1), and  $(t_i+1-t_i)$  will be measured in hours.

Specifically,

$$\begin{array}{l} AUC_{0\text{-}4h} = 0.5(y_0 + y_{0.5})/2 + 0.5(y_{0.5} + y_1)/2 + 0.5(y_1 + y_{1.5})/2 + 0.5(y_{1.5} + y_2)/2 \\ + 1(y_2 + y_3)/2 + 1(y_3 + y_4)/2 \end{array}$$

$$AUC_{0\text{-}2h} = 0.5(y_0 + y_{0.5})/2 + 0.5(y_{0.5} + y_1)/2 + 0.5(y_1 + y_{1.5})/2 + 0.5(y_{1.5} + y_2)/2$$

Two-hour MMTTs will be conducted at Visit 7/Week 8; Visit 8/Week 12; Visit 9/Week 16; Visit 10/Week 20; and Visit 12/Week 39; 4-hour MMTTs will be conducted at Screening; Visit 11/Week 26; and Visit 13/Week 52 or Early Termination. C-peptide results reported as  $\leq$ 0.1 ng/mL will be imputed as 0 for determination of the AUC0-4h and AUC0-2h.

An unscheduled MMTT time point measurement will be mapped to be a scheduled time point measurement for AUC calculation if: 1) A scheduled time point measurement is missing; and 2) The time of the unscheduled sample collection is within a 10-minute sampling window for that scheduled time point except for the last scheduled time point. Specifically, within 10 minutes after the start time of Boost Hi-Protein drink for the 0 minute time point; between 20 and 40 minutes after the 0 minute time point sampling, for the 30 minute time point; between 50 and 70 minutes after the 0 minute time point sampling, for the 60 minute time point; between 80 and 100 minutes after the 0 minute time point sampling, for the 90 minute time point; between 110 and 130 minutes after the

0 minute time point sampling, for the 120 minute time point; and between 170 and 190 minutes after the 0 minute time point sampling, for the 180 minute time point. If the last scheduled time point (120 minute time point for a 2-hour MMTT or 240 minute time point for a 4-hour MMTT) is missing and if there is an unscheduled time point that is after the last scheduled time point, the unscheduled measurement will be mapped to be the last time point measurement. For example, if the 240 minute time point is missing for a 4-hour MMTT, but there is a measurement at 270 minutes, then the measurement from the 270 minute time point will be used, with a time point value of 240 minutes.

After the mapping of unscheduled time point measurement(s), if any C-peptide measurement is still missing, the imputation rules specified in Section 7.2.4 will be applied.

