7.2. Mixed Meal Tolerance Test (MMTT) – Cohort 2 only

MMTTs are conducted after all other vital signs evaluations and laboratory tests have been collected. The MMTT test should only be started if the subject has been fasting for at least eight (8) hours. The MMTT may be rescheduled within the visit window if needed. All MMTT supplies will be provided by the Sponsor or designee. Basal exogenous insulin will be continued during the test, but any short-acting insulin will be withheld starting four hours prior to starting the test. Prior to initiating the MMTT, the subject's fasting glucose will be tested at the site and the value must be within 70-200 mg/dL to begin the MMTT. If the fasting glucose is not initially within range, the site may recheck levels while the subject is still at the clinic. If the fasting glucose remains outside of the allowed range, the subject must return to the site within the visit window and attempt the MMTT again.

An intravenous catheter can be placed in a patent vein in the subject's arm for the collection of blood samples. Insertion of the catheter should occur at least 30 minutes prior to any blood collections on the days MMTTs are performed. The subject should sit upright during the test. Slow walking is permitted, but vigorous exercise should be avoided.

Baseline, fasting blood samples are drawn for glucose and C-peptide within approximately five minutes prior to the start of the meal test. At time = 0, the subject drinks Boost® Hi-Protein (volume equal to 6 mL/kg body weight to a maximum of 360 mL). The entire drink must be ingested within 15 minutes.

For any visits requiring both an MMTT and an explant procedure, it is acceptable to perform the MMTT on a separate day up to 5 days prior to the explant procedure. Further details regarding MMTTs may be outlined in the study reference manual.

7.2.1. 4-Hour Mixed Meal Tolerance Test – Cohort 2 Only

The 4-hour MMTT is conducted only in Cohort 2 during Visit 2 (Week -4), Visit 11 (Week 26), and Visit 13 (Week 52 / Completion or ET). In addition to the time = 0 collection, samples for glucose and C-peptide are also collected at 30, 60, 90, 120, 180, and 240 minutes after the start of the Boost® meal test.

7.2.2. 2-Hour Mixed Meal Tolerance Test – Cohort 2 Only

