#### 7.2.6.3.2 Exogenous Insulin Independence

For subjects in Cohort 2, exogenous insulin independence will be defined in two ways.

First, achieving exogenous insulin independence will be defined as having an exogenous insulin dose of 0 for a minimum of any 14 consecutive days during the study, based on the data from exogenous daily insulin dose logs. Days that are missing or blank on the insulin log are not considered to be 0 values.

The second definition of exogenous insulin independence includes having an exogenous insulin dose of 0 for a minimum of any 14 consecutive days (the first definition of insulin independence) in addition to having HbA1c  $\leq$  7.0%, and (2-hour or 4-hour) MMTT fasting (at the start of the MMTT) glucose  $\leq$  125 mg/dL and 120-minute glucose  $\leq$  180 mg/dL. The HbA1c value and the MMTT glucose values will be those values obtained at a clinic visit that is closest temporally to the 14 consecutive days of 0 exogenous insulin dose. Depending on when the 0 doses of insulin begin, it is possible that the closest value temporally for HbA1c may be from a different clinic visit than the closest value temporally for glucose from the MMTT.

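### SAP 7.2.6.1 fills a missing 0-minute meal-test sample only from blood taken after the drink has started, although the protocol takes that sample before it; the rule is wrong as written, with a minor effect.

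*SAP*

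**What the plan says.** Protocol 7.2 places the 0-minute sample before the meal: "Baseline, fasting blood samples are drawn for glucose and C-peptide within approximately five minutes prior to the start of the meal test". The subject then drinks at time 0, and "The entire drink must be ingested within 15 minutes". Protocol 7.2.1 and 7.2.2 time the later samples from the start of the meal test.

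SAP 7.2.6.1 says when an unscheduled sample may replace a missing scheduled one in the AUC. The general condition is that it was collected "within a 10-minute sampling window for that scheduled time point". The SAP then gives each window. For the 0-minute point the sample must fall "within 10 minutes after the start time of Boost Hi-Protein drink for the 0 minute time point". For the next point it must fall "between 20 and 40 minutes after the 0 minute time point sampling, for the 30 minute time point"; the 60-, 90-, 120- and 180-minute windows follow the same two-sided pattern and use the same anchor. The last scheduled point of each test also has its own rule.

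Mapping comes first and imputation second: "if any C-peptide measurement is still missing, the imputation rules specified in Section 7.2.4 will be applied". For C-peptide, SAP 7.2.4 then says: "If the 0 minute timepoint is missing, the value will be imputed as zero". A missing first glucose is treated differently and becomes half of the first available value.

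**The concern.** The 0-minute window lies on the wrong side of the drink. It admits blood that the protocol would not call fasting, possibly drawn while the subject is still drinking. It leaves out pre-drink blood, which is what the protocol means by time 0. If a pre-drink C-peptide exists but is recorded as unscheduled and the scheduled result is missing, a measured value is set aside and a zero enters the AUC, including the primary Week 26 AUC0-4h.

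The anchor is a second fault in the same rule. The later windows are counted from the 0-minute sampling, so they cannot be evaluated when that sample was not taken and nothing has been mapped to it. If a late sample is mapped, they shift with it.

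**Working it through.** **Inputs.** The trapezoidal formula and sampling times (0, 0.5, 1, 1.5, 2, 3, 4 h) are from SAP 7.2.6.1. The reference figure of 0.8 ng·h/mL for a constant 0.20 ng/mL over 4 hours is from the protocol summary, Sample Size. The screening limit of 0.2 ng/mL is protocol exclusion criterion 30. Fasting values and curve shapes below are assumptions, because the documents give none.

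**Step 1: weights and the plan's own figure.** The formula gives weights of 0.25, 0.5, 0.5, 0.5, 0.75, 1.0 and 0.5 h for the 4-hour test, which sum to 4 h. A flat 0.20 ng/mL gives 0.20 × 4 = 0.80 ng·h/mL, which reproduces the protocol. The 2-hour weights are 0.25, 0.5, 0.5, 0.5 and 0.25 h (sum 2 h), giving 0.40.

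**Step 2: cost of the zero, flat profile.** With fasting value F, setting it to 0 removes 0.25 × F. As a share of the subject's own AUC this is 0.25/4 = 6.25% (0–4 h) or 0.25/2 = 12.5% (0–2 h), whatever F is. At F = 0.2 the AUC0-4h becomes 0.75 instead of 0.80. At F = 0.3, 0.5 and 1.0 ng/mL the loss is 0.075, 0.125 and 0.25 ng·h/mL. Results of 0.1 ng/mL or less are set to 0 anyway, so nothing changes there.

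**Step 3: rising profiles (assumed).** Let the 30-minute value be P and the seven values be F, P, 1.2P, 1.3P, 1.2P, 0.8P and 1.2F. A +10-minute sample, on a straight line from F to P, reads F + (P − F)/3.

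| F | P | True AUC0-4h | With zero | Change | +10-min value | With +10-min value | Change |
|---|---|---|---|---|---|---|---|
| 0.15 | 0.3 | 1.1625 | 1.125 | −3.2% | 0.200 | 1.175 | +1.1% |
| 0.2 | 0.4 | 1.550 | 1.500 | −3.2% | 0.267 | 1.567 | +1.1% |
| 0.3 | 0.9 | 3.360 | 3.285 | −2.2% | 0.500 | 3.410 | +1.5% |
| 0.5 | 1.5 | 5.600 | 5.475 | −2.2% | 0.833 | 5.683 | +1.5% |

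**Step 4: which substitute is worse.** Write P = kF. The error from a +10-minute sample is 0.25 × F × (k − 1)/3; the error from zero is 0.25 × F. Zero is worse whenever (k − 1)/3 < 1, that is, k < 4. The profiles above have k of 2 to 3.

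**Step 5: baseline.** If the fasting screening value does not exceed the 0.2 ng/mL limit on stimulated values, a zero at baseline moves the AUC by at most 0.25 × 0.2 = 0.05 ng·h/mL.

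**Step 6: anchor.** If a sample 10 minutes after the drink starts is mapped to time 0, the 30-minute window of 20–40 minutes after that sampling is 30–50 minutes after the drink starts. If nothing is mapped and no 0-minute sample was taken, the window has no starting time.

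**The case against.** The strongest reply is that the rule will seldom operate. The pre-meal blood that the protocol asks for is the scheduled 0-minute sample, and it enters the AUC at its nominal time without mapping. The window matters only if that result is missing and a separate unscheduled sample exists. The protocol schedules one pre-drink C-peptide for the AUC, and the ultrasensitive test is listed separately. No document shows how a second pre-drink result would arise, or how often. This stands and limits the size. The anchor problem is narrower still: it also needs a later scheduled sample to be missing and replaced by an unscheduled one.

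It could also be said that the general 10-minute condition may be read as two-sided. That does not stand, because the next sentence specifies the 0-minute window as after the drink starts.

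Three stronger readings are tempting and not supported.

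- A reader might divide the losses at fasting 0.3, 0.5 and 1.0 ng/mL by 0.8 ng·h/mL and infer 9%, 16% and 31%. But 0.8 is the AUC of a flat 0.2 ng/mL profile. A flat profile at 1.0 has an AUC0-4h of 4.0, so its loss is 6.25%.
- A reader might infer that a post-drink glucose becomes the "MMTT fasting (at the start of the MMTT) glucose" in the second insulin-independence definition. The mapping is stated for AUC calculation, and SAP 7.2.6.3.2 does not invoke it. The SAP is silent, which calls for a clarifying sentence and does not show an error.
- A reader might conclude that every post-drink sample should be barred. With the zero rule kept, Step 4 shows that this would increase the error whenever k is below 4.

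**Conclusion.** Wrong as written, minor. The 0-minute window contradicts the protocol's sampling time, and the later windows rest on a time that may not exist. When a scheduled 0-minute result is missing and a pre-drink sample is left unmapped, the AUC loses 0.25 h times the fasting C-peptide: 6.25% of AUC0-4h or 12.5% of AUC0-2h for a flat profile, and about 2–3% of AUC0-4h for the rising profiles assumed here. A mapped +10-minute sample instead adds about 1–1.5%, given a linear rise. At Week 26 the zero can only lower the measured response.

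The percentages rest on assumed curve shapes, and the number of tests affected cannot be derived from the documents. No hypothesis is tested and the secondary p-values are descriptive, so no formal conclusion depends on this. Cohort 2 has at most 40 subjects, divided by number of units implanted, so one mishandled test can still show in a small group's mean.

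**What to change.** In SAP 7.2.6.1:

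1. Extend the 0-minute mapping window to fasting samples taken up to 10 minutes before the drink starts, and give these precedence.
2. Keep an early post-drink sample (up to 10 minutes) for the AUC only when no pre-drink sample exists. State that it does not count as a fasting glucose in SAP 7.2.6.3.2.
3. Count the 30- to 180-minute windows from the drink start time, as protocol 7.2.1 does and as SAP 7.2.6.2 already does for time to response within a test.

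The cost is a few sentences in the SAP and the matching derivation code. No visit, sample or sample-size change is needed.

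### When the scheduled 240-minute MMTT draw is missing, the SAP accepts an unscheduled sample taken any time after 240 minutes but none taken just before it, so an imputed value can displace a near-exact measurement in the primary AUC0-4h

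*SAP*

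**What the plan says.** SAP 7.2.6.1 computes AUC0-4h by the trapezoidal rule at nominal times 0, 30, 60, 90, 120, 180 and 240 minutes. If a scheduled measurement is missing, an unscheduled one may replace it when it was taken "within a 10-minute sampling window for that scheduled time point except for the last scheduled time point". The listed windows end with "0 minute time point sampling, for the 120 minute time point; and between 170 and 190" minutes for the 180-minute point. No window is listed for 240 minutes.

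The last point (120 minutes in a 2-hour test, 240 in a 4-hour test) has a separate rule. It operates "if there is an unscheduled time point that is after the last scheduled time point", and in that case "the unscheduled measurement will be mapped to be the last time point measurement". No maximum delay is stated. In the SAP's example a test lacks its 240-minute sample but has one at 270 minutes; "then the measurement from the 270 minute time point will be used, with a time point value of 240 minutes".

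After mapping, "if any C-peptide measurement is still missing, the imputation rules specified in Section 7.2.4 will be applied". SAP 7.2.4 says of a missing final point that "it will be imputed as the average of the last available timepoint and zero". With only the 240-minute value missing, that is half the 180-minute value.

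The change in AUC0-4h from baseline to Week 26 is the Cohort 2 primary endpoint (SAP 7.3.6). The Week 52 change in the same quantity is secondary (SAP 4.2).

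**The concern.** The rule treats two similar departures in opposite ways and gives no reason. A sample 30 minutes late, three times the tolerance used elsewhere, is entered unchanged as the 240-minute value. A sample five minutes early, which is much closer to the target, is not used as that value.

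The 240-minute value carries weight 0.5 h in AUC0-4h, so an error there reaches the primary variable directly. The baseline value does not offset it. Protocol exclusion criterion 30 bars stimulated C-peptide above 0.2 ng/mL during screening, and SAP 7.2.6.1 sets results of 0.1 ng/mL or less to 0. Baseline AUC0-4h is therefore small, and an error at Week 26 passes almost whole into the change from baseline. Treatment groups are defined by the number of VC-01-DF units implanted, within at most 40 subjects. A single subject can therefore count for something in a group's least squares mean.

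**Working it through.** **Inputs.** Sampling times come from Protocol 7.2.1, the AUC formula and mapping rules from SAP 7.2.6.1, and the imputation rule from SAP 7.2.4. The documents give no post-implant C-peptide profile, so the profiles in steps 3 to 5 are assumptions.

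**1. The plan's own figure.** The protocol summary (sample size) gives an AUC of 0.8 ng x hour/mL for a constant 0.20 ng/mL over 4 hours. The SAP formula gives 0.20 x (0.5 + 0.5 + 0.5 + 0.5 + 1 + 1) = 0.20 x 4 = 0.800. It reproduces.

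**2. General form of the error.** The 240-minute value enters only the last trapezoid, 1 x (y180 + y240)/2. Hence error in AUC0-4h = 0.5 x (value entered - true y240). Under imputation this is 0.5 x (y180/2 - y240), which is negative when y240 is more than half of y180, zero at exactly half, and positive below half.

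**3. Flat profile at level c.** True AUC is 4c. Imputation enters 0.5c, so the loss is 0.5 x 0.5c = 0.25c, and 0.25c/4c = 6.25%. At c = 0.20, AUC falls from 0.800 to 0.750. This is an illustration and not a bound: a late-rising profile has more of its area in the last segments and would lose a larger share.

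**4. Assumed falling profile: 0.5, 1.0, 1.5, 1.8, 1.8, 1.4, 1.0 ng/mL.** The trapezoids are 0.375 + 0.625 + 0.825 + 0.900 + 1.600 + 1.200 = 5.525. A 235-minute value, interpolated between 1.4 and 1.0, is 1.4 - 0.4 x 55/60 = 1.033. A 270-minute value of 0.8 is assumed.

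| Value entered at 240 min | AUC0-4h | Error |
|---|---|---|
| 1.0 (true value) | 5.525 | 0 |
| 1.033 (235-minute sample used as it stands) | 5.542 | +0.3% |
| 0.7 (imputed, half of 1.4) | 5.375 | -2.7% |
| 0.517 (half of the 235-minute sample, if 7.2.4 counts it as last available) | 5.283 | -4.4% |
| 0.8 (270-minute sample entered as 240) | 5.425 | -1.8% |

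Now change only the true 240-minute value to 0.4. True AUC is 5.525 - 0.5 x 0.6 = 5.225, the imputed AUC is still 5.375, and the error is +0.15/5.225 = +2.9%.

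**5. Sensitivity.** A second assumed profile was 0.3, 0.6, 0.9, 1.0, 0.9, 0.7 ng/mL from 0 to 180 minutes, with exponential decline after that and y240/y180 from 0.3 to 1.0. Using a 235-minute sample errs by 0.0% to +0.4%. Imputing half of y180 errs by +2.5% (ratio 0.3), 0% (0.5), -2.4% (0.7) and -5.7% (1.0). Entering a 270-minute value as 240 errs by 0% to -1.8%.

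**6. The 2-hour test.** The list in SAP 7.2.6.1 gives 110 to 130 minutes for the 120-minute point without limiting it to 4-hour tests. Yet 120 minutes is also the exempted last point of a 2-hour test. The two statements conflict for a sample at, say, 115 minutes. AUC0-4h has no such ambiguity, because no window is listed for 240.

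**The case against.** A reader might infer that any final draw taken a few minutes early is thrown away. The documents do not support that. The mapping rule concerns unscheduled measurements and applies only when the scheduled one is missing. A draw at 235 minutes recorded under its 240-minute label is not missing and enters at its nominal time. The gap opens only when the site records the early draw as unscheduled and leaves the 240-minute field empty. This limitation stands in full, and it makes the case uncommon.

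A reader might also infer a systematic downward bias. That does not follow either. Imputation overstates the AUC when C-peptide falls by more than half between 180 and 240 minutes, and a late sample understates it only if C-peptide is still falling.

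The late rule can also be defended. In the SAP's 270-minute case on the falling profile, its result of 5.425 is closer to the true 5.525 than the imputed 5.375. What remains is the absence of any limit on lateness. A 300-minute value of 0.6 would give 5.325 (-3.6%), although nothing in the documents suggests that draws so late are expected.

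Finally, the effect on the trial result is small. One subject in 40 with an error of -0.15 against a mean of 5.525 moves the cohort mean by 0.15/40 = 0.00375, about 0.07%, though more within a small treatment group. SAP 7.1 states that no hypothesis is tested, so no power or error rate changes.

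**Conclusion.** The point holds as a minor defect in the derivation of the primary variable. For a 4-hour test with the scheduled 240-minute sample missing, a late unscheduled sample is accepted without limit. One taken just before 240 minutes is passed over in favour of an imputed value. For an affected subject, imputation gives -6.25% on a flat profile, -2.7% on the assumed falling profile, and an upward error when y240 is below half of y180. The SAP's own late case gives -1.8% on that falling profile. Using the early sample would err by well under 1% on the profiles tried.

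These sizes rest on assumed profiles. The documents do not say how often the situation will arise; few subjects are likely. The finding supports neither a claim of consistent bias nor any claim that the trial's conclusions are at risk. The case for acting is that the error is avoidable and the remedy is nearly free.

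**What to change.** In SAP 7.2.6.1:

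- Extend the 10-minute window to the last point: 230 to 250 minutes for the 240-minute sample.
- State that 110 to 130 minutes also applies to the 120-minute point when it ends a 2-hour test.
- For a sample later than the window, interpolate linearly to 240 (or 120) minutes between the last measured point and the late sample at its actual time. In the example, 1.4 at 180 and 0.8 at 270 minutes give 1.4 - 0.6 x 60/90 = 1.0, which restores 5.525. The match is exact only because the assumed profile is linear there.
- Use the 7.2.4 imputation only if neither kind of sample exists, and say in 7.2.4 whether an unmapped sample counts as the last available one.

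Interpolation brings actual times into an AUC otherwise computed at nominal times. If the sponsor prefers to avoid that, the symmetric window alone closes the early-sample gap, and a stated upper limit would be needed for late samples.

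The cost is a sentence or two in the SAP before database lock. No new data, visits or procedures are needed, and the existing windows already require the collection times of unscheduled samples.
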